Subjects who are transplanted with kidneys from HCV RNA-positive donors in Arm 1 will be followed for 1 year after the date of transplantation to evaluate safety, graft survival, mortality, allograft rejection, and potential hepatic and extrahepatic manifestations of HCV infection. All recipients of Arm 1 HCV RNA-positive kidneys will be assessed for SVR-12 after G/P treatment. Scheduled visits for subjects who accept an organ from HCV RNA-positive donors in Arm 1 and receive G/P treatment will consist of screening, day of transplant, day 1 of G/P treatment, week 1, week 2, week 4, week 6 and week 8 of treatment (planned end of treatment visit) after starting G/P. Additional scheduled visits will take place at weeks 4, 12 and 24 following completion of the G/P treatment and week 52 (1 year) after transplant. Subjects treated with G/P who experience virological failure will be evaluated for the emergence/persistence of direct-acting antiviral agent (DAA)-resistant viral variants, and suitable retreatment will be offered to study participants.

All subjects in study arm 2 will be followed for a minimum of 1 year from enrollment. In addition, subjects in study arm 2A who received a kidney from an HCV RNA-negative/HCV Ab-positive donor will be followed for a minimum of 24 weeks after the date of transplantation or 1-year post enrollment, whichever is longer, to evaluate safety, graft survival, mortality, and allograft rejection, and potential development of HCV viremia. Study visits for patients receiving a HCV RNA-negative/HCV Ab-positive kidney transplant in Arm 2A will take place at weeks 1, 4, 8, 12, and 24 weeks after transplantation. If a recipient of an HCV RNA-negative/HCV antibody-positive kidney in Arm 2A develops HCV infection within the first 24 weeks of follow-up after transplantation, that recipient will be offered treatment with G/P for 8 weeks. G/P treatment will be administered and subject will be followed as per local transplant center

standard-of-care and study-objective pertinent data from the G/P treatment period and post treatment period will be collected. This includes SAEs, treatment-emergent Grade 3 or greater laboratory abnormalities, and HCV RNA 12 weeks post G/P treatment completion.

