The primary efficacy endpoint is sustained virologic response 12 weeks post dosing (SVR₁₂), defined as HCV RNA < LLOQ 12 weeks after the last actual dose of G/P. The SVR₁₂ rate will be determined from all enrolled subjects who received an HCV RNA-positive kidney in Arm 1 and received at least one dose of G/P study drug along with a two-sided 95% confidence interval. The confidence interval for the SVR₁₂ rate will be calculated using Wilson's score method.

The secondary efficacy endpoints for recipients of kidney transplants from HCV RNA-positive donors in Arm 1 are:

1. The percentage of subjects with on-treatment virologic failure;
2. The percentage of subjects with post-treatment virologic relapse.

Additional efficacy analyses will be performed.

Clinical endpoints:

Secondary endpoints for the secondary objectives are:

1. Among all subjects enrolled in the study who receive a kidney transplant, the time to kidney transplant and cumulative incidence of each type of transplant will be determined for: study-eligible HCV RNA-positive kidneys (Arm 1), study-eligible HCV RNA-negative/HCV Ab-positive kidneys (Arm 2A), and standard of care kidney transplants (Arm 2B).
2. The number and percentage of subjects with clinical outcomes while on the

waitlist (SAEs, delisting from waitlist, death) among subjects who receive an HCV RNA-positive kidney in Arm 1 and among those subjects who do not receive a study eligible HCV RNA-positive kidney (all Arm 2 subjects) overall and with breakdown by the category in Arm 2 (2A, 2B and 2C). In addition, the total number of inpatient hospital days while on waitlist in those who did receive a study eligible HCV RNA-positive kidney (Arm 1) and total inpatient hospital days in those who did not (Arm 2) overall and with breakdown by categories of Arm 2 will be summarized descriptively.

3. The number and percentage of subjects with the following clinical outcomes and data post-transplant as applicable: death, graft failure, acute allograft rejection, delayed graft function, ALT elevations > 5x ULN, and SAEs. The difference in the overall percentage of subjects with clinical outcomes and data post-transplant between Arm 1 and Arms (2A + 2B1 – 2B4) will be assessed by logistic regression with Arm as a factor and appropriate covariates to adjust for possible differences between Arms including waiting list priority, blood group, geographic region and sensitization as appropriate.

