Subjects who are transplanted with kidneys from HCV RNA-positive donors in Arm 1 will be followed for 1 year after the date of transplantation to evaluate SVR12, SVR24, safety, death, graft failure, acute allograft rejection, delayed graft function, ALT elevation >5 times the upper limit of normal, eGFR and proteinuria. Specifically, scheduled in-person visits for subjects who received organs from HCV RNA-positive donors in Arm 1 and receive G/P treatment will consist of day of transplant, Day 1 of G/P treatment, weeks 1, 2, 4, and 8 (planned end of treatment visit) after starting G/P. Additional scheduled visits will take place at Post Treatment Week 4, Post Treatment Week 12, Post Treatment Week 24 (e.g., post G/P treatment visits) to evaluate SVR4, SVR12 and SVR24 and 1 year post transplant. The post-transplant study visit schedule for MYTHIC has been designed such that these visits should take place on the same days as standard of care clinical visits. For subjects in Arm 1 study-objective pertinent data will be collected while awaiting a transplant (ie, SAEs, hospitalizations, delisting from waitlist, death), and post-transplant (ie, death, graft failure, acute allograft rejection, delayed graft function, eGFR, proteinuria, ALT elevation >5 times the upper limit of normal, and SAEs). Subjects who experience virologic failure in

Arm 1 will be evaluated for the emergence/persistence of DAA-resistant viral variants, and suitable retreatment will be offered.

Study visits in Arm 2A will take place at weeks 1, 4, 8, 12, and 24 weeks after transplantation. Safety, graft survival, mortality, allograft rejection, and results of HCV RNA testing will be captured for a period of 24 weeks post-transplant. Study-objective pertinent data will be collected while awaiting a transplant (i.e., SAEs, delisting from waitlist, death), and post-transplant (i.e., death, graft failure, acute allograft rejection, delayed graft function, eGFR, proteinuria, ALT elevation >5 times the upper limit of normal, and SAEs). For subjects of Arm 1 and Arm 2A who become HCV infected, we will collect additional clinical outcomes of sclerosing cholestatic hepatitis and extrahepatic manifestations of HCV.

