Eligible subjects will initiate G/P 300 mg/120 mg QD for 8 weeks early after kidney transplantation. Day 3 post-transplant is targeted for the start of G/P treatment for HCV RNA-positive kidney recipients, with the conditions met that the subject should be out of the ICU, able to eat and drink and take medications orally, and in the judgement of the investigator, starting oral G/P treatment is safe for the subject.

A delay in commencing G/P after day 3 should only take place because the responsible site investigator and/or responsible clinicians believe that G/P cannot be safely administered or because of a high probability that G/P will subsequently need to be discontinued or held for prolonged period because the patient is likely to experience clinical deterioration. In the case of any patient who has not started G/P by day 3 after transplantation, the site investigator will discuss that case with the Principal Investigator [name], or delegate, and develop and document a plan to start G/P at a later time.

Post Treatment (PT) Period for recipients of HCV RNA-positive kidneys in Arm 1:

Subjects who complete or prematurely discontinue G/P treatment will be followed for 24 weeks after their last dose of study drug to evaluate efficacy and to monitor HCV RNA and the emergence and persistence of viral substitutions in the NS3 and NS5A, and subjects will be followed up at 1 year post the date of kidney transplant to assess graft function and survival and anti-HCV antibody serology.

Figure 1A: Overall Study Schematic

[figure not shown]
Treatment and PT Period for Study Arm 2A recipients of HCV RNA-negative/HCV antibody-positive kidneys:

Eligible subjects will be followed for 24 weeks after transplantation or 12 months after enrollment, whichever is longer, with surveillance for HCV infection using HCV RNA testing on week 1, week 4 (usual care), and week 24 (Figure 1B) after transplantation. A maximum number of up to n=20 subjects who are enrolled into the study can accept a study-eligible kidney from an HCV RNA-negative/HCV antibody-positive donor and be assigned to Arm 2A and will be followed in the study for 24 weeks post-transplant. The last study-eligible kidney transplant from an HCV RNA-negative/HCV antibody-positive donor in Arm 2A must occur no later than 24 weeks after the date of the 30th kidney transplant from an HCV RNA-positive donor in Arm 1 (see also section 5.1.5).

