Any subject in Arm 2A who develops HCV infection by 24 weeks after transplantation will be offered open-label G/P 300 mg/120 mg QD for 8 weeks. G/P will be provided by AbbVie, and while all patients will receive an 8-week course, the patient treatment visit schedule

and follow-up will be guided by the transplant center standard of care and AASLD/IDSA Guidelines for HCV treatment²⁶, and as described in section 5.1.1, 5.1.2 and Table 6. Outcome data, including SAEs, treatment emergent Grade 3 or greater laboratory abnormalities, sclerosing cholestatic hepatitis and extra-hepatic manifestations, and post-treatment week-12 HCV RNA will be collected from the subject medical record and entered into the study eCRFs. For kidneys from HCV RNA-negative/HCV Ab-positive donors in Arm 2A, the inclusion/exclusion criteria for donors are identical to donor inclusion/exclusion criteria as outlined in section 5.2.1 and 5.2.2, except that donor must be HCV RNA-negative.

Figure 1B: Schematic for patients undergoing transplantation with HCV RNA-negative/HCV antibody-positive kidney in Arm 2A

Observation period for other Study Arm 2 subjects

Enrolled Arm 2 subjects who were not transplanted will be followed for 1 year post enrollment and Arm 2 subjects who received an standard of care kidney (Arm 2B) will be

followed for a minimum of 1 year post-enrollment, or 24 weeks post transplantation whichever is longer, unless they are transplanted at a non-study site (Arm 2B5), in which case no further data will be collected after transplant.

5.1.1 Standard of Care Assessments for all patients – (patient managed clinically and billed per standard medical practice)

1. Subject assessment for kidney transplant candidacy, kidney transplantation, and follow-up care after transplant; prior HCV treatment history; medical history; co-morbid conditions; for-cause kidney biopsy or for cause liver biopsy, due to new or worsening symptoms of pre-transplant kidney or liver disease; or post-transplant delayed or decreasing kidney graft function with suspicion for FSGS, graft rejection, or suspicion for post-transplant fibrosing cholestatic hepatitis, or other new liver disease.
2. Donor kidney assessment and organ procurement, and including HCV RNA
3. Assessment of recipient and donor-organ match
4. G/P treatment regimen monitoring that takes place as part of SOC visits
5. Clinical factors (physical examinations, vital signs)
6. Adverse events and related safety management

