The investigator/clinician designee will evaluate whether the subject meets all of the eligibility criteria for the organ recipient specified in Section [5.2.1](#) and Section [5.2.2](#) and will record the results of this assessment and the details of the informed consent process in the subject's medical records and enter required subject data into the electronic case report form (eCRF) for this study. Enrolled patients will then enter the “waiting list phase.” Transplants will occur as deceased donor kidneys become available for consented patients and the study aims for accrual of 30 study-eligible kidney transplants from HCV-RNA positive donors. However, subjects who received a study-eligible HCV RNA-positive kidney offer and scheduled to be transplanted within 24 hours after the 30th HCV-RNA-positive kidney transplant will be allowed into Arm 1 of the study. Subjects who provided consent but do not receive an HCV RNA-positive organ offer will be actively followed in study Arm 2 for at least 1 year post enrollment, or 24 weeks post-transplantation, whichever is longer , unless they are transplanted at a non-study site (Arm 2B5), in which case no further data will be collected after transplant.

Medical records to support the medical history will be entered into the study electronic case report forms (eCRFs) developed by the Data Coordinating Center (DCC). Pre-specified information entered will include data from clinic visits, telephone contacts, relevant local laboratory testing and diagnostic/disease screening results (e.g. laboratory studies) collected as part of the standard medical care of the subject and relevant to their kidney transplant candidacy. The up-to-date data should also include sufficient medical history medications

to determine study candidacy. Older records (greater than 24 months) to document key medical history such as kidney disease and HCV treatment history may also be submitted.

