All adverse events will be collected and clinical outcomes, including death, graft failure, acute allograft rejection, delayed graft function, ALT elevation > 5 x ULN, SAEs, sclerosing cholestatic hepatitis and extrahepatic manifestations of HCV, and data of eGFR and proteinuria. An assessment for causality to transplant, HCV infection, or study drug G/P will be made. Grade 3 or greater treatment-emergent laboratory abnormalities from the first dose of G/P through 2 days post dosing will also be collected and summarized. Events of sclerosing cholestatic hepatitis and extrahepatic manifestations of HCV infection will only be collected in ARM 1 subjects and subset of ARM 2A subjects who develop HCV viremia.

Post-Treatment Phase in Arm 1

Post HCV treatment Phase: From 30 days post last dose of HCV treatment to 1 year post kidney transplant (last study visit), the following outcomes and other data will be collected: death, graft failure, acute allograft rejection, delayed graft function, ALT elevation > 5 x ULN, SAEs, sclerosing cholestatic hepatitis and extrahepatic manifestations of HCV. eGFR and proteinuria will be collected at specific visits. All SAEs will be assessed at every clinic visit when the subject is seen by a member of the study team.

All unresolved AEs considered possibly, probably, or definitely related to the study drug or to HCV infection should be followed by the investigator until the events are resolved, the subject is lost to follow-up, or the AE is otherwise explained.

The investigator will notify the IRB of any death or SAE occurring at any time after a subject has discontinued or terminated study participation that may reasonably be related to this study. The IRB will also be notified if the investigator should become aware of the development of cancer or of a congenital anomaly in a subsequently conceived offspring of a subject that has participated in this study.

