Clinical outcomes post-transplant will include death, graft failure, acute allograft rejection, delayed graft function, ALT elevation > 5 times the upper limit of normal, and SAEs. In addition, HCV-infection related events of fibrosing cholestatic hepatitis and extrahepatic manifestations of HCV infection collected for Arm 1 subjects and only for Arm 2A subjects who develop HCV viremia will also count as clinical outcomes. The number and percentage of subjects with each and any clinical outcomes will be summarized for those who receive an HCV RNA-positive kidney (Arm 1) versus Arm 2 subjects combined and broken down (2A and 2B) as applicable. The difference in the overall percentage of subjects with clinical outcomes post-transplant in Arm 1 vs Arm 2A + 2B will be assessed by logistic regression with Arm as a factor and including appropriate covariates to adjust for possible differences between Arms including waiting list priority, blood group,

geographic region and sensitization, as appropriate given sample size and other statistical considerations. In addition, to include any clinical outcomes due to being treated with G/P, another summary of clinical outcomes post-transplant will include any study drug (G/P) related severe treatment emergent adverse events for Arm 1 subjects, and another will include events of treatment emergent Grade ≥ 3 laboratory values and related severe treatment emergent adverse events as clinical outcomes for Arm 1 subjects.

Analyses of the eGFR outcome will be calculated eGFR using the 4-variable MDRD equation. Mean (SD) eGFR will be summarized at appropriate visits and compared between Arms. Specifically, mean eGFR at 24 weeks/6-months post-transplant and 1 year post transplant will be compared between Arm 1 transplant recipients and the combined group of Arm 2A and 2B transplant recipients (2B1-2B4). As a secondary approach, mean eGFR at 24 weeks/6-months post-transplant will be compared between Arm 1 recipients and Arm 2A and 2B kidney recipients limited to those 2A and 2B recipients who did not develop HCV infection.

We will also compare estimated proteinuria between Arms 1 and 2A, including a count of individuals with >1000 mg/day estimated proteinuria. Proteinuria will be estimated using spot protein:Cr ratio.

An exploratory analysis will summarize the number and percentage of subjects with clinical outcomes post kidney transplant for the subgroups of Arm 2B.

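### The post-transplant any-event logistic regression sets no common window and no time at risk, although Arm 1 is observed for a year after transplant and Arm 2A/2B may be observed for less, so it leans modestly against Arm 1

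*Protocol*

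**What the plan says.** **The analysis.** Protocol 8.1.4 compares the "overall percentage of subjects with clinical outcomes post-transplant in Arm 1 vs Arm 2A + 2B will be assessed by logistic regression". The Synopsis (Clinical endpoints, item 3) says the same difference "will be assessed by logistic regression with Arm as a factor and appropriate covariates", and limits the comparator to 2A plus 2B1-2B4. The named covariates are waiting list priority, blood group, region and sensitization. Neither place gives a window, an offset or a follow-up term. Section 8.1.4 refers to 6.1.4 for reporting periods, but 6.1.4 defines post-transplant periods for Arm 1 only. For eGFR, by contrast, 8.1.4 does fix time points (24 weeks/6 months and 1 year).

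**Arm 1 follow-up.** One year from transplant. Synopsis: "Subjects who are transplanted with kidneys from HCV RNA-positive donors in Arm 1 will be followed for 1 year after the date of transplantation". Section 5.1: "will be followed for 1 year after the date of transplantation to evaluate SVR12, SVR24, safety, death, graft failure". Section 6.1.4 collects the same outcomes up to the 1-year visit.

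**Arm 2 follow-up.** For Arm 2A, Section 5.1 says: "Eligible subjects will be followed for 24 weeks after transplantation or 12 months after enrollment, whichever is longer". For Arm 2B the observation-period paragraph of 5.1 says "followed for a minimum of 1 year post-enrollment, or 24 weeks post transplantation", the longer of the two. Section 5.1.3 says "followed in study Arm 2 for at least 1 year post enrollment, or 24 weeks post-transplantation, whichever is longer", and 5.1.10 agrees. The opening paragraph of 5.1, however, attaches the 24-week floor to Arm 2A only. The Synopsis and a later paragraph of 5.1 mention just 12 months or more from enrolment for standard-of-care recipients.

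**SAP.** Protocol 8.1 leaves details to the SAP. The draft SAP has no row for the any-event composite and does not withdraw it. Part 15 models SAEs as recurrent events by a rate model. Parts 10 to 14 (death, graft failure, delayed graft function, rejection, ALT) concern Arm 1 only.

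**The concern.** A yes/no endpoint of the form any event since transplant grows with the length of observation. If one group is watched for 52 weeks and the other for somewhere between 24 and 52, the percentages differ even when the risks are equal. The direction is known: against Arm 1, whenever a first event can fall after Arm 2 observation has ended. None of the named covariates corrects for this.

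The between-arm part of secondary objective 3 is at stake. Recipients of HCV RNA-positive kidneys could appear to do worse partly because they were watched longer. There is a smaller asymmetry in the same regression: fibrosing cholestatic hepatitis and extrahepatic HCV events count for Arm 1 and for viremic 2A subjects, but are not collected in 2B.

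**Working it through.** The documents give no expected rate, sample size or power for this comparison, so there is no planned figure to reproduce. The check is an illustration with no true difference between arms.

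**Inputs from the Protocol**
- Arm 1 n = 30, two-sided 5% test (5.1.5, 8.1).
- Transplant pace: 40 of 90 (44%) within about 6 months (8.2).
- About 40% readmitted within 30 days of transplant (9.4.1).

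**Assumptions**
- Wait from enrolment to transplant is exponential at the 8.2 pace: rate = -ln(0.56)/26 = 0.0223 per week.
- Arm 2 minimum follow-up is taken as actual: f = max(24, 52 - wait) weeks.
- A share e = 0.40 to 0.60 has an event by day 30 (the upper value allows for delayed graft function). After that the rate is r = 0.25 to 1.0 per year. The documents do not support any particular r.
- For t of at least 30 days, P(event by t) = 1 - (1 - e) x exp(-r(t - 30)/365).

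**Comparator numbers, matched to the waits**
- Waits up to 26 weeks: 40 - 30 = 10 comparators. Mean Arm 2 follow-up is 40.2 weeks and nobody has under 26, so the floor plays no part.
- Waits up to 52 weeks: 90 x (1 - 0.56²) = 61.8 transplants, less 30, gives about 32 comparators. Mean Arm 2 follow-up is 34.5 weeks, against 52 in Arm 1.

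**Example** (e = 0.40, r = 1.0, waits up to 52 weeks). Arm 1 at day 364: 1 - 0.60 x exp(-334/365) = 0.760. Arm 2 averaged over f: 0.658. Odds ratio = (0.760/0.240)/(0.658/0.342) = 1.65.

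Rejection is by exact enumeration of the unadjusted pooled two-proportion z-test, standing in for the covariate-adjusted regression.

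| e | r | Arm 1 | Arm 2, waits ≤26 wk | OR | Reject (n=10) | Arm 2, waits ≤52 wk | OR | Reject (n=32) |
|---|---|---|---|---|---|---|---|---|
| 0.40 | 0.25 | 0.523 | 0.495 | 1.12 | 5.7% | 0.480 | 1.19 | 7.0% |
| 0.40 | 0.5 | 0.620 | 0.574 | 1.21 | 6.1% | 0.549 | 1.34 | 8.9% |
| 0.40 | 1.0 | 0.760 | 0.696 | 1.38 | 7.7% | 0.658 | 1.65 | 14.1% |
| 0.60 | 0.25 | 0.682 | 0.663 | 1.09 | 5.3% | 0.653 | 1.14 | 5.7% |
| 0.60 | 0.5 | 0.747 | 0.716 | 1.17 | 5.8% | 0.699 | 1.27 | 7.0% |
| 0.60 | 1.0 | 0.840 | 0.797 | 1.33 | 6.2% | 0.772 | 1.55 | 10.6% |

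**Milder conditions (waits up to 52 weeks)**
- e = 0.80: rejection 5.5% to 7.0% with 32 comparators.
- Half of Arm 2 followed to 52 weeks, half to the minimum: OR 1.07 to 1.30, rejection 5.2% to 6.9% with 10 comparators and 4.8% to 6.5% with 20 (an assumed intermediate number).

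**Common 24-week window.** The odds ratio is 1.00 by construction. Rejection is 4.9% to 5.4% (n = 10) and 5.2% to 5.6% (n = 32).

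**Precision.** With p the 24-week risk (0.454 to 0.726), the 95% CI factor for the odds ratio is exp(1.96 x sqrt((1/30 + 1/n)/(p(1 - p)))). This is 4.2 to 5.0 for n = 10 and 2.7 to 3.1 for n = 32.

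**The case against.** **The SAP has moved on.** Each component of the composite has its own SAP row, none of them a between-arm any-event percentage, and Part 15 handles time at risk for SAEs, which probably dominate. This is the strongest point. But the composite is in the Protocol as a planned test, and the draft SAP is silent on it. A reader might infer that silence means withdrawal; nothing in the SAP says so.

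**Minimum follow-up is not actual follow-up.** This is correct. The Arm 2 periods are minima, and 8.1.4 plans a 1-year eGFR comparison that includes 2A and 2B1-2B4, so some Arm 2 data at a year are expected. If half of Arm 2 reaches 52 weeks, rejection is close to nominal.

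**First events come early.** This is also fair. Delayed graft function and early readmission both count, and with 80% affected by day 30 little bias remains. The upper end of the table depends on 1.0 event per year, which has no source in the documents.

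**Other problems are larger.** Arm 2B has no donor-quality limit and includes living donors, so a common window would not make the arms comparable. That is true, but it is no reason to leave in a bias that a sentence can remove.

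**Stronger readings to avoid.** A reader might infer that all of Arm 2 stops at 24 weeks. One sentence in 5.1 on Arm 2A data capture suggests this for that group, but the follow-up rules give the longer of two periods. A reader might also infer that 2B has no post-transplant floor. Only the opening of 5.1 points that way: at least 12 months from enrolment does not exclude a longer period, and three other places state the floor. Finally, severe G/P-related events and Grade 3 or higher laboratory values do not enter this regression; 8.1.4 puts them in separate summaries.

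**Conclusion.** The point holds in a limited form. As written, the composite regression compares cumulative percentages over unequal periods, and with equal true risk it leans against Arm 1 whenever first events can fall after Arm 2 observation ends. Under the stated assumptions the spurious odds ratio lies between about 1.1 and 1.65, and the rejection rate between about 5% and 14%. The upper values need long waits, minimum follow-up taken as actual, and a high late event rate.

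The documents do not support a claim that the trial's safety conclusion is compromised. The objective is secondary, mainly descriptive and non-randomised, no decision rule rests on it, and the confidence interval is wider than the bias. SVR12 is not affected. The flaw is still worth correcting before analysis, because its direction is known and the correction is cheap.

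**What to change.** 1. State in the SAP whether the composite is kept or dropped.
2. If kept, count events by onset date from transplant to day 168 in Arm 1, 2A and 2B1-2B4. Use only outcomes collected in all of them: death, graft failure, acute rejection, delayed graft function, ALT above 5 times ULN, and SAEs. Time from transplant to first such event, censored at end of follow-up, is an acceptable alternative.
3. Report fibrosing cholestatic hepatitis and extrahepatic HCV events descriptively, outside the between-arm test.
4. Reconcile the opening of 5.1, and the 12-month wording in the Synopsis and later in 5.1, with the observation-period paragraph of 5.1, 5.1.3 and 5.1.10, so that 2B1-2B4 data reach day 168. Use the Synopsis comparator (2A plus 2B1-2B4) in 8.1.4.

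**Cost.** Wording changes, and some chart abstraction for 2B subjects transplanted late in their first year. With the day-168 cut, Arm 1 events after week 24 become descriptive only. The window removes the follow-up bias but not differences in ascertainment (Arm 1 liver tests are ordered as study labs where not standard care, while 2B outcomes come from the medical record) or in donor mix, and the comparison stays imprecise.
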